### **2.5.3.2 Algorithm for Determining Analysis Visit Windows for Efficacy Observations**

For the efficacy assessment, the reference date for the derivation of relative days of events or findings will be D1 selection visit.

Selected efficacy variables will be summarized by the following analysis window:

- EDSS (assessed every 6 months from TOPAZ Day 1 to TOPAZ Month 60, at End of Study (EOS) visit, and at unscheduled visits.)
- SF-36, FAMS and EQ-5D (assessed yearly from TOPAZ Day 1 to TOPAZ Month 60, and at End of Study (EOS) visit.)
- MRI assessments (assessed yearly from TOPAZ Day 1 to TOPAZ Month 60, and at End of Study (EOS) visit.)

The algorithm for determining analysis visit windows and the observations to be used in the safety analyses will be applied to the above efficacy assessments in a similar manner. For efficacy analyses, all visits up to the end of the study, including those outside the protocol specified windows will be included.

### **2.5.4 Unscheduled visits**

Unscheduled MRI scans EDSS and questionnaires will be assigned to the appropriate analysis window. Otherwise, only scheduled visit efficacy measurements will be used for by visit analysis to exclude the temporary fluctuations in the clinical status that may occur with a relapse.

Laboratory and vital sign data from unscheduled visits will be used in PCSA and descriptive analysis. The unscheduled visits will also be assigned to the appropriate analysis time for the summary of change from baseline by visit. The one closest to the targeted visit date will be used in the presence of multiple measurements within the same time window.

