### **9.6 EFFICACY MEASUREMENTS**

#### **9.6.1 Relapse**

Relapse is defined as new neurological symptoms or worsening of previous neurological symptoms with an objective change on neurological examination. Symptoms must be attributable to MS, last at least 48 hours, be present at normal body temperature (ie, no infection, excessive exercise, or excessively high ambient temperature), and be preceded by at least 30 days of clinical stability.

EDSS must be completed to confirm the relapse.

If the MS relapse is confirmed, the therapeutic approach will be decided by the Study Investigator, and all the treatments will be described in the e-CRF. Patients will be followed up at the discretion of the Study Investigator and all the procedures and assessments will be collected in the e-CRF.

MS relapse will be verified at each visit. On the other hand, patients will be informed to contact the Study Investigator as soon as they observe any sign/symptom compatible with a possible relapse, in order to schedule an extra visit (see [Section 10.1.4](#)).

Relapses will not be considered as AEs (see [Section 10.4.1.2](#)).

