### 1.3 DETERMINATION OF SAMPLE SIZE

There are no sample size calculations for this long-term safety study. Sample size will be based on elective participation of patients who were enrolled (and completed at least 48 months) into the CAMMS03409 extension study.

[figure not shown]

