### **2.1.3.2 Expanded Disability Status Scale (EDSS)**

Patient disability will be evaluated using the EDSS, which has long been considered the standard for assessing disability in patients with MS.

EDSS will be collected at D1 (if not collected in the previous 3 months) and then at each scheduled visit (every 6 months) and unscheduled visits for MS relapse. For the change from baseline in EDSS analysis, unscheduled EDSS assessments will not be used (except for early study discontinuation assessments).

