#### *2.4.4.1.3 EDSS*

The observed value, change from baseline as well as percentage change from baseline will be presented descriptively. The change from baseline in EDSS will be analyzed using a mixed model for repeated measures (MMRM) (7)(8)(9) with baseline EDSS score, analysis group indicator (IAT and DAT), geographic region, study visit and study visit by analysis group interaction as covariates. The TOPAZ study baseline at study entry is considered as post-baseline for efficacy analysis. The comparison of the change from baseline in EDSS with the MMRM will include the change from baseline to each consecutive year which can be constructed using the linear contrasts of the estimated regression parameters. All post-baseline EDSS scores will be included in the MMRM; patients without any post-baseline scores will not be included. For this model, imputation will not be used.

Similar analysis for change of EDSS by alemtuzumab courses and for retreated population will be analyzed as well.

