If only one record is within an analysis visit window, the data from that record will be used in the summary statistics and by visit analyses. If more than one record is within the same analysis visit window, the record from the regularly scheduled visit will be used in the summary statistics and by visit analyses. If more than one record is from a regularly scheduled visit, or more than one record is from unscheduled visits within the same analysis visit window, the record from the visit nearest to the middle of the interval will be used in the summary statistics and by visit analyses. If two visits are “tied” before and after the middle of the interval, the later record will be used in the summary statistics and by visit analyses. If the scheduled visit does not have any record but the windowed unscheduled visit is in an analysis visit window, data from the unscheduled visit will be used for the summary statistics and by visit analyses.

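### The SAP gives conflicting rules on unscheduled EDSS scores, so relapse-time scores can enter the EDSS change model against the plan's stated intent

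*SAP*

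**What the plan says.** Five places in the SAP bear on whether an unscheduled EDSS score is analysed.

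- **SAP 2.1.3.2** collects EDSS "at each scheduled visit (every 6 months) and unscheduled visits for MS relapse", then sets the exclusion: "For the change from baseline in EDSS analysis, unscheduled EDSS assessments will not be used (except for early study discontinuation assessments").
- **SAP 2.5.4** states: "Unscheduled MRI scans EDSS and questionnaires will be assigned to the appropriate analysis window". The next sentence opens with *otherwise* and restricts by-visit efficacy analyses to scheduled measurements. The reason it gives is to keep out short-lived changes around a relapse.
- **SAP 2.5.3.1** gives the scheduled record priority within a window. Where the scheduled visit has no record, "data from the unscheduled visit will be used for the summary statistics and by visit analyses". It also assigns early-withdrawal visits to windows.
- **SAP 2.5.3.2** applies that algorithm to efficacy. Of the three efficacy items it lists, only EDSS is shown as also assessed at unscheduled visits.
- **SAP 2.4.4.1.3** states: "All post-baseline EDSS scores will be included in the MMRM". It does not repeat the exclusion, and it uses no imputation.

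The affected records will exist. Protocol 9.6.1 says "EDSS must be completed to confirm the relapse", and Protocol 10.1.5 includes EDSS in the minimum set for any unscheduled visit.

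**The concern.** A score taken to confirm a relapse is likely to be higher than the same patient's stable score. If such scores stand in for scheduled ones, the estimated long-term change in disability moves towards worsening. The SAP says in two places (2.1.3.2 and the second sentence of 2.5.4) that it wants to avoid this, yet other current sections let the scores in.

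There is also a problem of reproducibility. A programmer who follows 2.1.3.2 and one who follows 2.5.4 with 2.5.3.1 and 2.5.3.2 would build different analysis datasets. EDSS is part of the IAT versus DAT comparison that SAP 2.4.4 calls the main long-term efficacy analysis. It is also among the yearly outputs in SAP section 3, so an unresolved choice could be made differently from year to year.

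**Working it through.** **No plan figure to reproduce.** The SAP states "There are no sample size calculations for this long-term safety study", and neither document gives an EDSS standard deviation, an expected relapse rate, a transient rise or a missing-visit rate. The check is therefore a comparison of the rules, followed by a size illustration on assumed inputs.

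**Step 1. One case under each rule.** A patient misses the scheduled Month 18 EDSS but has an unscheduled relapse EDSS at Month 17. The six-monthly window runs from Month 15 to Month 21.

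| Rule | Is the Month 17 score used in the change analysis? |
|---|---|
| 2.1.3.2 | No |
| 2.5.4, first sentence | Yes, assigned to the Month 18 window |
| 2.5.4, second sentence | No, by its stated purpose; but it covers only what the first sentence has not already admitted |
| 2.5.3.1 via 2.5.3.2 | Yes, because the window has no scheduled record |
| 2.4.4.1.3 | Yes, if *all* is taken literally |

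If the scheduled Month 18 score were present, 2.5.3.1 would use it and drop the Month 17 score. Only the literal reading of 2.4.4.1.3 would keep both.

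**Step 2. Inputs (all assumed).**
- Annualized relapse rate (ARR): 0.1 to 0.3
- One unscheduled EDSS per relapse, so the expected number per six-month window is r = ARR/2 = 0.05 to 0.15
- Transient rise d: 0.5 to 1.5 points
- Share of scheduled EDSS missing, m: 5% to 15%, independent of relapse

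**Step 3. Window filling (2.5.3.1 and 2.5.3.2).** A relapse score is used only when the scheduled one is missing. Its share of analysed scores is m·r / ((1 − m) + m·r), and the shift in the mean is that share times d.
- Low: 0.05 × 0.05 = 0.0025; 0.0025 / 0.9525 = 0.26%; × 0.5 = 0.001 points
- Middle: 0.10 × 0.10 = 0.01; 0.01 / 0.91 = 1.1%; × 1.0 = 0.011 points
- High: 0.15 × 0.15 = 0.0225; 0.0225 / 0.8725 = 2.6%; × 1.5 = 0.039 points

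**Step 4. Pooling every score (2.4.4.1.3 read literally).** The share is r / (1 + r), with no scheduled score missing.
- Low: 0.05 / 1.05 × 0.5 = 0.024 points
- Middle: 0.10 / 1.10 × 1.0 = 0.091 points
- High: 0.15 / 1.15 × 1.5 = 0.196 points

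The pooled figures are about 5 to 18 times the window-filling figures (0.196 / 0.039 and 0.0238 / 0.0013).

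**Step 5. Group contrast.** The bias in IAT minus DAT is the shift in IAT minus the shift in DAT. It is zero if both groups have the same r, m and d. Even with one group at the high case and the other at the low case, it is 0.039 − 0.001 = 0.038 points under window filling, and 0.196 − 0.024 = 0.172 under pooling.

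**The case against.** The best defence is that 2.1.3.2 governs. It is the only sentence that names unscheduled EDSS in the change-from-baseline analysis, and the second sentence of 2.5.4 shares its purpose. On that view 2.5.4 is poorly worded rather than a clean rule to include. The sentence in 2.4.4.1.3 sits beside statements on which patients contribute and on imputation. The model has study visit as a factor, which presupposes one record per visit.

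Much of this stands. A reader might infer that most of the SAP's rules simply admit relapse scores, or that a shift of up to 0.20 points is to be expected. The documents do not support either inference: 2.5.4 is divided against itself, 2.5.3.1 puts the scheduled record first, and the larger range needs the most literal reading of 2.4.4.1.3.

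The assumption of one unscheduled score per relapse is also generous, because relapses are verified at scheduled visits too. Nor is every unscheduled score relapse-driven, since Protocol 10.1.5 allows an extra visit whenever the investigator finds it necessary.

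The defence does not remove the conflict. The SAP states no order of precedence, 2.5.4 names EDSS among the measures to be windowed, and 2.5.3.2 brings EDSS under the fill-in rule without exception. A programmer has to choose.

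**Conclusion.** The conflict is real and lies in current SAP text. Following 2.5.4, 2.5.3.1 and 2.5.3.2 as written would admit relapse-time scores that the SAP says it wants to leave out.

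The likely effect is small: about 0.001 to 0.04 EDSS points under window filling, on the assumptions listed. The range of 0.02 to 0.20 is an upper case that applies only if every unscheduled score is pooled. If patients in relapse tend to have the extra visit instead of the scheduled one, missingness and relapse are linked and the first range is too low. The documents give nothing from which to estimate that.

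A reader might also infer that the IAT versus DAT contrast is biased. That does not follow. EDSS uses TOPAZ data plus the prior-study baseline (SAP 2.4.4), and by then both groups have received alemtuzumab (SAP 2.3.3). The contrast is affected only if relapse, missed visits or the size of the rise differ between groups during TOPAZ, and the documents show no such difference.

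EDSS is a secondary endpoint in a non-comparative study for which Protocol 11.4 plans no formal hypothesis tests. The point should be fixed because the correction is simple, but it does not threaten the study's primary safety objective.

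**What to change.** Make SAP 2.1.3.2 the single rule and align the other sections with it.

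1. **2.5.4:** delete EDSS from the first sentence.
2. **2.5.3.2:** state that an unscheduled EDSS does not fill an empty window, except for early-discontinuation assessments, which are still windowed under 2.5.3.1. Without this exception the change would conflict with 2.1.3.2.
3. **2.4.4.1.3:** define the MMRM input as all scheduled post-baseline EDSS scores plus the early-discontinuation assessment.

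Unscheduled EDSS then serves relapse confirmation. A sensitivity analysis that adds the unscheduled scores is optional.

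The cost is SAP wording, with no new data or visits. A few windows stay empty, which the MMRM handles without imputation. The change does not remove transient worsening altogether: a scheduled EDSS that happens to fall during a relapse remains in the analysis.

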### **2.5.5 Pooling of centers for statistical analyses**

Not applicable.

### **2.5.6 Statistical technical issues**

Not applicable.

### 3 INTERIM ANALYSIS

A yearly interim analysis is planned for this study. Only data collected in TOPAZ study will be used for this interim analysis. Generally, demographic and disposition of patients, summary of safety results, and summary of efficacy results will be provided.

For safety, key safety results including TEAE, SAE, AESI, death, AEs leading to treatment discontinuation along with related laboratory values and vital sign values in which details are provided in [Section 2.4.5](#) will be provided in the interim analysis report. For efficacy, the interim analysis is performed for EDSS, relapse and MRI related efficacy endpoints and Quality of life outcomes in which details are provided in [Section 2.4.4](#). Summary of demographics and disposition of patients will also be provided.

## **4 DATABASE LOCK**

The database is planned to be locked approximately at 6 months after first patient completed 5 years of follow-up.

## **5 SOFTWARE DOCUMENTATION**

All summaries and statistical analyses will be generated using SAS version 9.0 or higher.

## 7 LIST OF APPENDICES

[Appendix A](#): Potentially clinically significant abnormalities (PCSA) criteria

## Appendix A Potentially clinically significant abnormalities criteria

### CRITERIA for POTENTIALLY CLINICALLY SIGNIFICANT ABNORMALITIES for Phase 2/3 studies (oncology excepted) (Version 3.0 May 2014)

Parameter	PCSA	Comments
Clinical Chemistry		
ALT	By distribution analysis : >3 ULN >5 ULN >10 ULN >20 ULN	Enzymes activities must be expressed in ULN, not in IU/L. Concept paper on DILI - FDA draft Guidance Oct 2007. Internal DILI WG Oct 2008. Categories are cumulative. First row is mandatory. Rows following one mentioning zero can be deleted.
AST	By distribution analysis : >3 ULN >5 ULN >10 ULN >20 ULN	Enzymes activities must be expressed in ULN, not in IU/L. Concept paper on DILI – FDA draft Guidance Oct 2007. Internal DILI WG Oct 2008. Categories are cumulative. First row is mandatory. Rows following one mentioning zero can be deleted.
Alkaline Phosphatase	>1.5 ULN	Enzymes activities must be expressed in ULN, not in IU/L. Concept paper on DILI – FDA draft Guidance Oct 2007. Internal DILI WG Oct 2008.
Total Bilirubin	>1.5 ULN >2 ULN	Must be expressed in ULN, not in µmol/L or mg/L. Categories are cumulative. Concept paper on DILI - FDA draft Guidance Oct 2007. Internal DILI WG Oct 2008.
Conjugated Bilirubin	>35% Total Bilirubin and TBILI>1.5 ULN	Conjugated bilirubin dosed on a case-by-case basis.
ALT and Total Bilirubin	ALT>3 ULN and TBILI>2 ULN	Concept paper on DILI - FDA draft Guidance Oct 2007. Internal DILI WG Oct 2008. To be counted within a same treatment phase, whatever the interval between measurements.

**CRITERIA for POTENTIALLY CLINICALLY SIGNIFICANT ABNORMALITIES  
for Phase 2/3 studies (oncology excepted)  
(Version 3.0 May 2014)**

Parameter	PCSA	Comments
CPK	>3 ULN >10 ULN	FDA Feb 2005. Am J Cardiol April 2006. Categories are cumulative. First row is mandatory. Rows following one mentioning zero can be deleted.
CrCl (mL/min) (Estimated creatinine clearance based on the Cockcroft-Gault equation)	<15 (end stage renal disease) ≥15 - <30 (severe decrease in GFR) ≥30 - < 60 (moderate decrease in GFR) ≥60 - <90 (mild decrease in GFR) ≥90 (normal GFR)	FDA draft Guidance 2010 Pharmacokinetics in patients with impaired renal function-study design, data analysis, and impact on dosing and labeling
eGFR (mL/min/1.73m2) (Estimate of GFR based on an MDRD equation)	<15 (end stage renal disease) ≥15 - <30 (severe decrease in GFR) ≥30 - < 60 (moderate decrease in GFR) ≥60 - <90 (mild decrease in GFR) ≥90 (normal GFR)	FDA draft Guidance 2010 Pharmacokinetics in patients with impaired renal function-study design, data analysis, and impact on dosing and labeling
Creatinine	≥150 µmol/L (Adults) ≥30% change from baseline ≥100% change from baseline	Benichou C., 1994.
Uric Acid Hyperuricemia Hypouricemia	>408 µmol/L <120 µmol/L	Harrison- Principles of internal Medicine 17 th Ed., 2008.
Blood Urea Nitrogen	≥17 mmol/L	
Chloride	<80 mmol/L >115 mmol/L	
Sodium	≤129 mmol/L ≥160 mmol/L	
Potassium	<3 mmol/L ≥5.5 mmol/L	FDA Feb 2005.
Total Cholesterol	≥7.74 mmol/L	Threshold for therapeutic intervention.
Triglycerides	≥4.6 mmol/L	Threshold for therapeutic intervention.
Lipasemia	≥3 ULN	

**CRITERIA for POTENTIALLY CLINICALLY SIGNIFICANT ABNORMALITIES  
for Phase 2/3 studies (oncology excepted)  
(Version 3.0 May 2014)**

Parameter	PCSA	Comments
Amylasemia	≥3 ULN	
Glucose		
Hypoglycaemia	≤3.9 mmol/L and <LLN	ADA May 2005.
Hyperglycaemia	≥11.1 mmol/L (unfasted); ≥7 mmol/L (fasted)	ADA Jan 2008.
HbA1c	>8%	
Albumin	≤25 g/L	
CRP	>2 ULN or >10 mg/L (if ULN not provided)	FDA Sept 2005.
Hematology		
WBC	<3.0 GIGA/L (Non-Black); <2.0 GIGA/L (Black) ≥16.0 GIGA/L	Increase in WBC: not relevant. To be interpreted only if no differential count available.
Lymphocytes	>4.0 GIGA/L	
Neutrophils	<1.5 GIGA/L (Non-Black); <1.0 GIGA/L (Black)	International Consensus meeting on drug-induced blood cytopenias, 1991. FDA criteria.
Monocytes	>0.7 GIGA/L	
Basophils	>0.1 GIGA/L	
Eosinophils	>0.5 GIGA/L or >ULN (if ULN ≥0.5 GIGA/L)	Harrison- Principles of internal Medicine 17 th Ed., 2008.
Hemoglobin	≤115 g/L (Male); ≤95 g/L (Female) ≥185 g/L (Male); ≥165 g/L (Female)  Decrease from Baseline ≥20 g/L	Criteria based upon decrease from baseline are more relevant than based on absolute value. Other categories for decrease from baseline can be used (≥30 g/L, ≥40 g/L, ≥50 g/L).
Hematocrit	≤0.37 v/v (Male) ; ≤0.32 v/v (Female) ≥0.55 v/v (Male) ; ≥0.5 v/v (Female)	
RBC	≥6 Tera/L	Unless specifically required for particular drug development, the analysis is redundant with that of Hb. Otherwise, consider FDA criteria.
Platelets	<100 GIGA/L ≥700 GIGA/L	International Consensus meeting on drug-induced blood cytopenias, 1991.

**CRITERIA for POTENTIALLY CLINICALLY SIGNIFICANT ABNORMALITIES  
for Phase 2/3 studies (oncology excepted)  
(Version 3.0 May 2014)**

Parameter	PCSA	Comments
Urinalysis		
pH	≤4.6 ≥8	
Vital signs		
HR	≤50 bpm and decrease from baseline ≥20 bpm ≥120 bpm and increase from baseline ≥20 bpm	To be applied for all positions (including missing) except STANDING.
SBP	≤95 mmHg and decrease from baseline ≥20 mmHg ≥160 mmHg and increase from baseline ≥20 mmHg	To be applied for all positions (including missing) except STANDING.
DBP	≤45 mmHg and decrease from baseline ≥10 mmHg ≥110 mmHg and increase from baseline ≥10 mmHg	To be applied for all positions (including missing) except STANDING.
Orthostatic Hypotension		
Orthostatic SDB		
Orthostatic DBP	≤-20 mmHg ≤-10 mmHg	
Weight	≥5% increase from baseline ≥5% decrease from baseline	FDA Feb 2007.

Signature Page for VV-CLIN-0578573 v1.0  
lps13649-16-1-9-sap

Approve & eSign

Approve & eSign

Approve & eSign

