## 4 INTRODUCTION AND RATIONALE

Multiple sclerosis (MS) is a demyelinating disease of the central nervous system (CNS) that affects approximately 2.5 million people worldwide (1). Its clinical course is typically characterized by initial episodes of transient neurological compromise with full recovery, followed by a phase of cumulative deficits that may increase with each new episode. Most relapsing patients eventually develop secondary progression leading to a constellation of chronic sequelae including profound muscle weakness, impaired gait and mobility, bladder and bowel dysfunction, and cognitive and visual impairments.

MS is believed to arise from the interplay of polygenic inherited susceptibility and as yet unidentified environmental agents. Age of onset typically ranges from 10 to 59 years, with most cases occurring between 20 and 40 years of age. As with most other autoimmune disorders, MS is more than twice as common among women. Pathologically, MS is characterized by focal and non-focal tissue injury of the brain and spinal cord due to the complex interplay of inflammation, demyelination, axonal injury, astrogliosis, and tissue atrophy. Lymphocytes are believed to play a central role in MS pathogenesis.

Alemtuzumab (Lemtrada®) is a humanized monoclonal antibody that binds to CD52, a cell surface antigen present at high levels on T and B lymphocytes, and at lower levels on natural killer cells, monocytes, and macrophages (2).

There is little or no CD52 detected on neutrophils, plasma cells, or bone marrow stem cells. Alemtuzumab acts through antibody-dependent cellular cytotoxicity and complement mediated lysis following cell surface binding to T and B lymphocytes.

The mechanism by which alemtuzumab exerts its therapeutic effects in MS is unknown, but may involve immunomodulation through the depletion and repopulation of lymphocytes.

Research suggests that potential immunomodulatory effects in MS may include alterations in the number, proportions, and properties of some lymphocyte subsets post-treatment (3).

Pilot studies in MS patients were conducted at Addenbrooke's Hospital in the United Kingdom (UK). Genzyme Corporation (Genzyme, a Sanofi company) has sponsored Phase 2 and Phase 3 randomized, comparator-controlled studies in patients with relapsing remitting MS that have established superior efficacy for alemtuzumab compared with subcutaneous interferon beta-1a (SC IFNB-1a, Rebif®) on clinical and imaging endpoints (4, 5, 6, 7, 8).

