#### **11.4.2 Analyses of safety data**

All patients in the study will be evaluated for safety. A summary of safety will be evaluated based on incidence, duration, grade/intensity, seriousness, and relationship of AEs to study drugs, and on changes in physical examination, vital signs, and clinical laboratory results, particularly hematological parameters and biochemical, immunological, and clinical indications of ITP, infection, and thyroid dysfunction observed in this study. Deaths and other SAEs will also be evaluated. Particular attention will be paid to the development of autoimmune disorders including the incidence of ITP, autoimmune thyroid disorders and anti-GBM disease. Further elaboration of statistical issues will be provided in the SAP.

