#### **2.1.4.3 Laboratory safety variables**

Clinical laboratory data consists of blood analysis, including hematology, clinical chemistry, and urinalysis. Clinical laboratory values after conversion will be analyzed into standard international units and international units will be used in all listings and tables.

For patients exposed to alemtuzumab within 48 months prior to inclusion in this study, samples for clinical laboratories will be taken at monthly for CBC with differential (including platelet count), serum creatinine, liver function and urinalysis. TSH must be obtained every 3 months and HPV test should be performed yearly until 48 months after the last infusion of alemtuzumab administered in the study CAMMS03409.

For patients exposed to alemtuzumab during this study, pregnancy test, HPV test must be obtained before the infusion in TOPAZ study if they were not done within 12 months prior to the treatment. CBC with differential (including platelet count), serum creatinine, TSH, liver function test (ALT, AST, ALP, albumin, total protein, direct bilirubin and total bilirubin) and urinalysis (minimally including determination of urine protein and red blood cells) with microscopy are also required to be assessed before alemtuzumab infusion if they were not assessed within 2 weeks prior to treatment. Samples for CBC with differential (including platelet count), serum creatinine, liver function and urinalysis will be analyzed monthly. The TSH will be performed quarterly. The HPV test will be performed yearly. In addition, unscheduled liver function tests may be performed at any time if clinically indicated at Investigators' discretion.

The laboratory parameters will be classified as follows:

- Hematology
  - **Red blood cells and platelets and coagulation:** hemoglobin, hematocrit, red blood cell count, platelet count
  - **White blood cells:** white blood cell count, neutrophils, lymphocytes, monocytes, basophils, eosinophils
- Clinical chemistry
  - **Renal function:** creatinine, creatinine clearance
  - **Liver function:** alanine aminotransferase, aspartate aminotransferase, alkaline phosphatase, total protein, albumin, direct bilirubin and total bilirubin

- TSH

Urine samples will be collected minimally including determination of urine protein and red blood cells with microscopy.

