#### **2.4.5.3 Analyses of laboratory variables**

Laboratory analysis will be conducted for retreated population and 48 months follow-up population. The baselines for each population are defined as below.

- Retreated population baseline: The last non-missing assessment prior to first dose of alemtuzumab in TOPAZ study. The baseline should be taken within 2 weeks prior to the treatment for laboratory assessment except for HPV and pregnancy test. For HPV and pregnancy test, it can be taken in 12 months before the treatment.
- 48 months follow-up population baseline: The last non-missing assessment prior to the last dose of alemtuzumab in previous studies. The baseline should be taken within 2 weeks

prior to the treatment for laboratory assessment except for HPV and pregnancy test. For HPV and pregnancy test, it can be taken in 12 months before the treatment.

The summary statistics (including number, mean, median, Q1, Q3, standard deviation, minimum and maximum) of all laboratory variables (central laboratory values and changes from baseline) will be calculated for each visit or study assessment (baseline, each postbaseline time point, last on-treatment and/or worst on-treatment value and/or other specific assessment) in overall group and by subgroups (IAT vs DAT). This section will be organized by biological function [Section 2.1.4.3](#).

The incidence of PCSAs (list provided in [Appendix A](#)) at any time during the treatment-emergent adverse event period will be summarized by biological function and in overall group and by subgroups (IAT vs DAT) whatever the baseline level and/or according to the following baseline status categories:

- Normal/missing
- Abnormal according to PCSA criterion or criteria

For parameters for which no PCSA criteria are defined, similar table(s) using the normal range will be provided.

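### Lymphocytes have only a high abnormality criterion, which also shuts off the normal-range fallback, so no table counts patients with laboratory-defined low lymphocytes

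*SAP*

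**What the plan says.** SAP 2.1.4.3 lists the white-cell parameters to be analysed: "white blood cell count, neutrophils, lymphocytes, monocytes, basophils, eosinophils". SAP 2.4.5.3 then plans two kinds of laboratory output for the re-treated and 48-month follow-up populations: summary statistics by visit, and the incidence of PCSAs at any time in the treatment-emergent period.

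The PCSA limits come from a generic sponsor list in SAP Appendix A, dated May 2014. Its lymphocyte row reads "Lymphocytes >4.0 GIGA/L", and the comment column is empty. In the same table neutrophils, hemoglobin, hematocrit and platelets all have low limits.

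SAP 2.4.5.3 adds a fallback: "For parameters for which no PCSA criteria are defined, similar table(s) using the normal range will be provided". For baseline status it uses two groups: normal or missing, and "Abnormal according to PCSA criterion or criteria".

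On the drug, Protocol section 4 says that the therapeutic mechanism is unknown but "may involve immunomodulation through the depletion and repopulation of lymphocytes". It also says that the antibody binds T and B lymphocytes and acts by cytotoxicity and lysis. Protocol 9.1 makes changes in laboratory parameters a primary endpoint.

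**The concern.** The fallback is there so that a parameter without a sponsor limit still gets an incidence table. It is triggered by parameter, not by direction. A parameter with a limit on one side only is therefore treated as fully covered, and the other side gets no table. For lymphocytes the uncovered side is the low one, which is the side on which this drug is expected to act.

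A programmer who follows the text would count a patient with persistently low lymphocytes after re-treatment as having no lymphocyte abnormality. The only patients in that row would be those above 4.0 GIGA/L. The report on a primary safety endpoint could then show little or no lymphocyte abnormality in a population treated with a lymphocyte-depleting antibody, and a reader could not tell from the incidence tables how many patients were low or when.

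**Working it through.** The plan states no figure on this point, so there is none to reproduce. The check applies the Appendix A rules to example counts.

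**Inputs from the SAP (GIGA/L).** Lymphocyte PCSA: above 4.0. Low WBC PCSA: below 3.0 (non-Black), below 2.0 (Black). Neutrophil PCSA: below 1.5 (non-Black), below 1.0 (Black).

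**Assumptions, not in the documents.** Other white cells total 0.65 (monocytes 0.4, eosinophils 0.2, basophils 0.05). Lower limit of normal (LLN) for lymphocytes: 0.8, 1.0 or 1.5, used only to show a range.

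**Step 1: the lymphocyte row.** The tested counts of 0.1, 0.3, 0.5, 0.8, 1.0, 1.5 and 4.0 are all unflagged; 4.1 is flagged. Against any of the three assumed LLNs, 0.1, 0.3 and 0.5 would be low.

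**Step 2: the fallback.** It requires that no PCSA criterion be defined. One is defined, so there is no normal-range table.

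**Step 3: baseline status.** A low baseline count does not meet the above-4.0 criterion. With two groups available, it can only go to normal/missing. Re-treatment implies earlier exposure, so low baseline counts are plausible.

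**Step 4: can low WBC stand in?** With L for lymphocytes and N for neutrophils, WBC = L + N + 0.65.

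| L | N | WBC | Lymphocyte PCSA | Low WBC PCSA (non-Black) | Neutrophil PCSA (non-Black) |
|---|---|---|---|---|---|
| 0.1 | 2.0 | 2.75 | no | yes | no |
| 0.3 | 2.0 | 2.95 | no | yes | no |
| 0.5 | 2.0 | 3.15 | no | no | no |
| 0.1 | 4.0 | 4.75 | no | no | no |
| 4.1 | 2.0 | 6.75 | yes | no | no |

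For non-Black patients the low WBC flag needs L + N + 0.65 < 3.0, so L + N < 2.35. At L = 0.1 it fires only if N < 2.25; at L = 0.5, only if N < 1.85. For Black patients it needs L + N < 2.0 − 0.65 = 1.35. Whether a low lymphocyte count is caught therefore depends on the neutrophil count, and a flagged WBC does not say which cell line is low. The WBC comment also says "To be interpreted only if no differential count available", and Protocol 9.5.2 and 10.1.6.2 require a monthly differential.

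**Step 5: the other outputs.**
- By-visit statistics (mean, median, quartiles, minimum, possibly worst value) describe the distribution. They do not count patients below a limit. SAP 2.4.5.3 calls them central laboratory values, whereas Protocol 10.1.6.2 sends the samples to local laboratories, so their content needs clarifying too.
- Adverse event tables would show reported lymphopenia. Under Protocol 10.4.2, however, a laboratory abnormality becomes an adverse event only if it is symptomatic, needs treatment or consultation, changes dosing, is serious, or is an event of special interest.
- Patient listings (Protocol 11.4) contain the values but no count.

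**The case against.** The best defence is that low lymphocytes are not invisible. Quartiles by visit show whether at least a quarter, half or three quarters of patients lie below a given level, and a worst-value summary would describe the nadir. Some low counts trip the WBC criterion: in the table, lymphocytes of 0.1 and 0.3 with neutrophils of 2.0 both do. The WBC comment limits interpretation and does not delete the row. It also follows a remark about WBC increases, so its scope is unclear. The study is descriptive with no formal tests, and investigators review each result as it arrives.

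All of that stands, and it rules out several stronger readings that a reader might infer:
- That no low lymphocyte value reaches any PCSA table. The low WBC row contradicts this.
- That lymphopenia appears nowhere in the report. Statistics, listings and reported events remain.
- That the protocol specifically promised a lymphopenia analysis. Protocol 11.4.2 says "particularly hematological parameters and biochemical, immunological, and clinical indications of ITP, infection, and thyroid dysfunction", which does not name lymphopenia. Cytopenias are events of special interest only under autoimmune conditions, so expected depletion by the drug is not clearly among them.
- That 48 monthly differentials per patient are affected in both populations. The 48-month follow-up population enters part-way through that period (SAP 2.3.1.2), and follow-up after re-treatment may run past the end of the study.

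The defence does not supply a count of patients below a lymphocyte limit, and none of the outputs that it cites provides one.

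**Conclusion.** The gap is real but narrow. Read literally, the SAP produces no table of how many patients have laboratory-defined low lymphocytes, and it places low baseline counts under normal/missing. This follows from the wording of the two rules and needs no assumption. The WBC illustration rests on an assumed 0.65 GIGA/L for other cells and serves only to show that low WBC is an incomplete and non-specific substitute.

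How many patients are affected cannot be computed, because the documents give neither lymphocyte data nor a lower limit of normal. This is a reporting gap in a primary safety endpoint. It does not affect the data collected or the monitoring of patients, and it can be closed without new data.

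**What to change.** In SAP 2.4.5.3, reword the fallback so that it works by direction: where a parameter has no PCSA criterion on one side, tabulate it against the normal range on that side. For lymphocytes this gives a below-LLN row by baseline status, with a low baseline shown as its own group instead of under normal/missing. Produce it for the re-treated and 48-month follow-up populations.

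Present the lymphocyte row by time since last infusion, with patients assessed in each interval as the denominator, and not only at any time. Early depletion is expected, so an any-time row alone would largely record that expected effect and would not show who is still low later.

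The cost is a few extra rows and one by-time display, using differentials already collected monthly. Two practical points apply. Local laboratory ranges must be in the database; the criteria expressed in multiples of the upper limit of normal already presuppose this for other parameters. The reworded rule also reaches other one-sided parameters (monocytes, basophils, eosinophils and red cells are high-only as well), so the SAP may name any direction that it chooses not to tabulate. No new clinical threshold is needed.
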